Substantial Modification(s)		
Clarified the timing of primary analysis (primary completion date).	A sample size of 90 participants randomized and who received Year 1 IP in the study provides >95% power (assuming a delta of 3 from baseline in the NSAA total score; SD=3.5) to address the primary objective of the trial; this allows for the primary analysis to be conducted when at least 90 treated participants have completed Day 360 (Visit 19).	Sections 4.1. Overall Design. 9.3. Populations for Analysis. 9.5.. Interim Analyses.
Provided instructions that participants who decline Year 1 IP administration will be withdrawn from the study, and that those who decline Year 2 IP administration but remain in the study will not attend Visit 18 (if applicable), Visits 20 to 30.2 or receive protocol-mandated glucocorticoid regimen. Prohibited concomitant medications do not apply to these participants.	To ensure follow-up while avoiding hospitalization, the very frequent safety visits post Year 2 IP administration, and the receipt of high doses of glucocorticoids, given that there is no acutely increased risk of an immune reaction.	Section 7.2.1. Withdrawal of Consent. 1.3.1. Schedule of Activities – Year 1 (Screening to Year 1 Day 360), footnote “f”. Also, in Appendices 10.9. Italy, 10.10. Japan, 10.14. Germany,

Description of Change	Brief Rationale	Section # and Name
		10.15. Russia and 10.16. Israel. Section 1.3.2. Schedule of Activities – Year 2 and Long Term Follow Up, footnotes “bb” and “cc”. Also, in Appendices 10.9. Italy, 10.10. Japan, 10.14. Germany, 10.15. Russia and 10.16. Israel.
Non-substantial Modification(s).		
Replaced Estimand 1 (Treatment Policy) with the Primary Estimand for the primary endpoint. Clarified that death or loss of ambulation are identified as potential intercurrent events.	Updated based on US FDA Type D meeting feedback received on 26 June 2023.	Sections 1.1. Synopsis. Section 3.1. Efficacy Objectives,

Description of Change	Brief Rationale	Section # and Name
		Estimands, and Endpoints. Section 9.1.1. Estimands
Replaced Estimand 1 (Treatment Policy) for secondary endpoints with Secondary Estimand(s). Clarified that death or loss of ambulation are identified as potential intercurrent events.	Updated based on US FDA Type D meeting feedback received on 26 June 2023.	Sections 1.1 Synopsis. Section 3.1. Efficacy Objectives, Estimands, and Endpoints. Section 9.1.1. Estimands.
Removed Estimand 2 (Hypothetical) for the primary endpoint.	Updated based on US FDA Type D meeting feedback received on 26 June 2023 indicating challenges with interpretation of the hypothetical Estimand.	Sections 1.1 Synopsis. Section 3.1. Efficacy Objectives, Estimands, and Endpoints. Section 9.1.1. Estimands.
Updated “FAS” to “FAS (through Week 52)” and added definition of Efficacy Analysis Set (long-term)	Clarification that FAS analysis would be through Week 52 (double-blind period). Added definition for “Efficacy Analysis Set (Long-term)”, the analysis population to be used for long term efficacy analysis in the study.	Section 9.3. Populations for Analysis.
Clarified the p-value boundary to be used for secondary endpoints that are part of the gatekeeping procedure.	Clarified to preserve study wise Type-I error rate (across primary and secondary endpoints).	Section 1.1. Synopsis. Section 9.1. Estimands and Statistical Hypotheses.

Description of Change	Brief Rationale	Section # and Name
Clarified that instructions for the management of SAEs of elevated troponin or myocarditis are provided in Sections 8.2.7 and 8.2.8.	To ensure that relevant instructions are easily accessed.	Section 9.5.1. Data Monitoring Committee.
Clarified that GLDH is not considered sensitive clinical data.	To clarify that ALT/AST but not GLDH kept blinded from sites and from the sponsor on Day 9 in Year 1 and Year 2.	Section 1.3.1 1.3.1. Schedule of Activities – Year 1 (Screening to Year 1 Day 360), footnote “aa”. Section 1.3.2 1.3.2. Schedule of Activities – Year 2 and Long Term Follow Up, footnote “x”. Country Appendices: 9 (Italy), 10 (Japan), 14 (Germany), 15 (Russia) and 16 (Israel).
Deleted a statement indicating that the primary analysis would be performed when all enrolled participants complete one year of observation following treatment. Deleted information regarding follow up in the study.	To align with other sections in the protocol. The information deleted from Section 2.1 is not part of the rationale for the study.	Section 1.1. Synopsis. Section 2.1. Study Rationale.
Inserted Section 10.10.8 and clarified that for sites in Japan the	To correct an omission in the country appendix.	Appendix 10 (Japan), Section

Description of Change	Brief Rationale	Section # and Name

1. PROTOCOL SUMMARY

1.1. Synopsis

Short Title: A Phase 3, Randomized, Double-Blind, Placebo-Controlled Study of PF-06939926 in DMD.

Rationale

The purpose of the study is to demonstrate the safety and efficacy of fordadistrogene movaparvovec (PF-06939926) treatment in participants with DMD to support regulatory review for marketing authorization.

Objectives, Estimands, and Endpoints

The primary objective of the study is to demonstrate superior efficacy of treatment with fordadistrogene movaparvovec as compared to placebo. The table below describes the primary and secondary objectives, estimands, and endpoints. Additional exploratory objectives and endpoints address data collected after the time of the primary analysis including those for participants receiving fordadistrogene movaparvovec in Year 2 (Cohort 2) and those collected in the long-term follow-up.

Objectives	Endpoints	Estimands
Primary:	Primary:	Primary:
To demonstrate superior efficacy of treatment with fordadistrogene movaparvovec as compared to placebo based on change from Baseline in the North Star Ambulatory Assessment (NSAA).	Change from Baseline at Week 52 in the NSAA total score.	Primary Estimand: Population: Boys with a genetic diagnosis of DMD who are ambulatory and age ≥ 4 to < 8 years; Variable: Change from Baseline at Week 52 in the NSAA total score; Death or loss of ambulation are identified as potential intercurrent events. Population-level summary: difference in mean changes from Baseline at Week 52 in the NSAA total score between fordadistrogene movaparvovec and placebo.
Secondary:	Secondary:	Secondary:
To quantify the mini-dystrophin expression level in the muscle of participants treated with	Change from Baseline in percent normal mini-dystrophin expression level in biceps brachii muscle biopsies at Day 360 using a	Secondary Estimand(s):

Objectives	Endpoints	Estimands
fordadistrogene movaparvovec.	liquid chromatography mass spectrometry (LC-MS) assay.	Population: Boys with a genetic diagnosis of DMD who are ambulatory and age ≥ 4 to < 8 years; Variable: Each secondary endpoint; Death or loss of ambulation are identified as potential intercurrent events. Population-level summary: difference in means between fordadistrogene movaparvovec and placebo for each secondary endpoint.
To characterize the distribution of mini-dystrophin expression in the muscle of participants treated with fordadistrogene movaparvovec.	Change from Baseline in percent of muscle fibers expressing mini-dystrophin in biceps brachii muscle biopsies at Day 360 as assessed by immunofluorescence.	
To characterize the change in serum creatine kinase (CK) concentration in participants treated with fordadistrogene movaparvovec as compared to placebo.	Change from Baseline at Week 52 in serum CK concentration.	
To characterize the skills gained, based on the individual items of the NSAA, in participants treated with fordadistrogene movaparvovec as compared to placebo.	Number of skills gained at Week 52 based on the individual items of the NSAA.	
To characterize the skills either improved or maintained, based on the individual items of the NSAA, in participants treated with fordadistrogene movaparvovec as compared to placebo.	Number of skills either improved or maintained at Week 52 based on the individual items of the NSAA.	
To characterize the 10-meter run/walk velocity in participants treated with fordadistrogene movaparvovec as compared to placebo.	Change from Baseline at Week 52 in the 10 meter run/walk velocity.	
To characterize the rise from floor velocity in participants treated with fordadistrogene	Change from Baseline at Week 52 in the rise from floor velocity.	

Objectives	Endpoints	Estimands
movaparvovec as compared to placebo.		
To characterize the functional health status in participants treated with fordadistrogene movaparvovec as compared to placebo.	Change from Baseline at Week 52 in the Modified Pediatric Outcomes Data Collection Instrument (PODCI): Transfer and Basic Mobility Core Scale (Pediatric Parent).	
	Change from Baseline at Week 52 in the Modified PODCI: Sports and Physical Functioning Core Scale (Pediatric Parent).	

Overall Design

This is a Phase 3, global, multi-center, randomized, double-blind, placebo-controlled study in ambulatory male participants, ages ≥ 4 to <8 years, with a genetic diagnosis of DMD who are on a stable daily regimen of glucocorticoids. Eligible participants will be randomized into Cohort 1 or Cohort 2 in a 2:1 fashion and stratified by their age at Screening (<6 or ≥ 6 years old). Study enrollment will be managed to ensure that no more than approximately 55% of dosed participants are in either of the Screening age strata. Enrollment will be assessed periodically, and if an imbalance is noted, then enrollment of the overrepresented stratum may be paused until a more balanced distribution is achieved. Cohort 1 (approximately 66 participants) will receive a single dose of fordadistrogene movaparvovec on Day 1 (Visit 3) and a single dose of placebo at Day 390 (Visit 20). Cohort 2 (approximately 33 participants) will receive a single dose of placebo on Day 1 (Visit 3) and a single dose of fordadistrogene movaparvovec at Day 390 (Visit 20), if they remain eligible.

Number of Participants

A sufficient number of participants will be screened to achieve a total of approximately 99 participants in the FAS across two strata (age <6 years and age ≥ 6 years) with no more than approximately 55% of dosed participants in either of the Screening age strata.

This sample size is based on the primary efficacy endpoint of change from Baseline at Week 52 in the NSAA total score. The above sample size (assuming 3 participants will drop out of the study prior to Week 52) will provide 98% power to detect a treatment difference (fordadistrogene movaparvovec – placebo) of 3.0. These calculations are based on $\alpha=0.05$ (two-sided), a 3-look group-sequential design with a gamma family (-1) spending function to determine the efficacy boundary, a gamma family (-4) spending function for the non-binding futility boundary, a common standard deviation of 3.5, and using the normal approximation of the test statistic for the comparison between two means.

Screen failures are defined as participants who consent to participate in the clinical study but are not subsequently randomized to a cohort.

Intervention Groups and Duration

In the context of this study, treatment will consist of two single intravenous infusions, one of fordadistrogene movaparvovec and one of placebo. Fordadistrogene movaparvovec will be administered as a dose of 2E14 vg/kg. The term investigational product (IP) is used to refer to either fordadistrogene movaparvovec or placebo. A single intravenous infusion of IP will be delivered over approximately 2 to 4 hours with the timing and sequence as follows:

- Cohort 1 will receive a single dose of fordadistrogene movaparvovec on Day 1 (Visit 3) and a single dose of placebo at Day 390 (Visit 20);
- Cohort 2 will receive a single dose of placebo on Day 1 (Visit 3) and a single dose of fordadistrogene movaparvovec at Day 390 (Visit 20), if they remain eligible.

All participants will be followed for 5 years after the administration of fordadistrogene movaparvovec such that total time on study will be approximately 5 years for Cohort 1 and 6 years for Cohort 2.

Data Monitoring Committee: Yes

An external data monitoring committee (E-DMC) will be used to provide an ongoing objective, unblinded assessment of safety and efficacy.

Statistical Methods

Primary Estimand: For the primary analysis, change from Baseline at Week 52 in the NSAA total score will be analyzed using a mixed model repeated measures approach including visits through Week 52 where NSAA is assessed. Baseline NSAA total score is defined as the last non-missing NSAA total score collected prior to Year 1 IP administration. The analysis will be based on the Full Analysis Set (FAS) (regardless of adherence to glucocorticoid regimen) and missing data will not be explicitly imputed. The model will include fixed effects for treatment (class variable), visit (class variable), treatment by visit interaction, Baseline NSAA total score (continuous variable), Screening age (continuous variable), Baseline NSAA total score by visit interaction, and Screening age by visit interaction with an unstructured covariance matrix to describe the correlation among different visits from the same participant. Alternative covariance structures to address any issues with model convergence will be specified in the statistical analysis plan (SAP). Estimates at Week 52 of the mean changes from Baseline and 95% confidence intervals along with the mean treatment group difference, two-sided p-value, and two-sided 95% confidence interval for the mean difference will be provided.

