Completion of Year 2	Day 449 (Visit 31) to Day 749 (Visit 35)	Routine safety monitoring; Efficacy assessments; Viral vector shedding.
Long-Term Follow-up Year 3 to Year 6	Day 930 (Visit 36) to Day 2190 (Visit 43)	Routine safety monitoring; Efficacy assessments; Viral vector shedding; Muscle biopsy (Day 1830).*

Table 1. Brief Overview of the Study Periods

Study Period	Days and Visits	Overview of Main Tests/Procedures
--------------	-----------------	-----------------------------------

* First ~15 participants (with the potential to collect a maximum of 33 if needed) from selected sites. The post-Baseline muscle biopsies will be performed on Day 360 and Day 1830.

** For participants who undergo Day 328 (Visit 18) during a study dosing pause, the amount of IP to be shipped to the site will be determined once the study has been restarted. Therefore, the weight collected at Day 328 (Visit 18) will not be entered into the interactive response technology drug management system during the study dosing pause. Participants will be evaluated for Year 2 IP eligibility when the study is restarted.

The primary analysis will occur after at least 90 FAS participants complete Day 360 (Visit 19) or discontinued from the study prior to Week 52 if they had received Year 1 IP at least one year prior to the data cutoff. After the database has been released for the primary analysis, the study may become fully unblinded.

Investigators in Japan should see [Section 10.10 \(Appendix 10\)](#) for details on the interval between IP administration for consecutive participants.

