9.2. Sample Size Determination

A sufficient number of participants will be screened to achieve a total of approximately 99 participants in the FAS (see Section 9.3). Participants will be randomly assigned in a 2:1 fashion to Cohort 1 (approximately 66 participants) or Cohort 2 (approximately 33 participants) across the two strata (age <6 years and age \geq 6 years). This sample size is based on the primary efficacy endpoint of change from Baseline at Week 52 in the NSAA total score. The above sample size (assuming 3 participants will drop out of the study prior to Week 52) will provide 98% power to detect a treatment difference (fordadistrogene movaparvovec – placebo) of 3.0. These calculations are based on $\alpha=0.05$ (two-sided), a common standard deviation of 3.5 and using the normal approximation of the test statistic for the comparison between two means. Assuming both interim analyses will be performed (3 looks) and a gamma family alpha-spending function with gamma parameter -1 for efficacy will be used to control Type I error, the probability of crossing the boundary at the first interim analysis is 38%, at the second interim analysis is 78%, and at the primary analysis is 97%. A gamma family spending function with gamma parameter -4 will be used for the non-blinding futility boundary.

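### The Synopsis attributes 98% power to the three-look design; 98% is the power without interim analyses, and the three-look design has 97%, as Section 9.2 states

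*Protocol*

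**What the plan says.** Protocol Section 1.1 (Synopsis, Number of Participants) plans about 99 participants in the full analysis set (FAS), allows for 3 dropouts before Week 52, and says this "will provide 98% power to detect a treatment difference"; the effect is a "treatment difference (fordadistrogene movaparvovec – placebo) of 3.0". The next sentence gives the bases: two-sided alpha of 0.05 and "a 3-look group-sequential design with a gamma family (-1) spending function to determine the efficacy boundary". It adds non-binding futility with gamma family (-4) spending, an SD of 3.5 in both arms and a normal approximation.

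Section 9.2 (Sample Size Determination) repeats the 98% for the same sample size, effect and dropout, but its list of bases names only alpha, the SD and the normal approximation. It then takes the case in which both interims are performed, with the same gamma family (-1) spending, and gives the probability of crossing the efficacy boundary as 38% at the first interim, then "at the second interim analysis is 78%, and at the primary analysis is 97" per cent. These three figures sum to more than 100%, so they must be cumulative, and the last one is the power of the three-look design.

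Section 9.5 makes both interims optional, at about 30 and about 60 FAS participants with Week 52 data. On timing, Section 4.1 says: "The primary analysis will occur after at least 90 FAS participants complete Day 360 (Visit 19) or discontinued from the study".

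**The concern.** The two sections give different powers for the same design. The Synopsis lists three looks and both spending functions as bases of the 98%. Section 9.2 attaches 98% to a calculation with no interims and 97% to three looks. Repeated looks within a fixed overall alpha cost some power at a given maximum sample size, so one label has to be wrong.

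What is at stake is modest. The Synopsis is where most readers find the power of this registrational trial, and it should carry the right figure for the design it names. No decision in the protocol turns on the difference.

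**Working it through.** **Inputs, all from the Protocol.** Difference 3.0, SD 3.5, two-sided alpha 0.05, allocation 2:1, 99 less 3 = 96 evaluable, so 64 against 32 (Sections 1.1 and 9.2). Interims at 30 and 60 (Section 9.5). Efficacy spending gamma family -1; non-binding futility spending gamma family -4.

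**Step 1: reproduce the 98%.** The expected value of the test statistic is

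drift = 3.0 / (3.5 × √(1/64 + 1/32)) = 3.0 / (3.5 × 0.2165) = 3.959.

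Power of a single analysis = Φ(3.959 − 1.960) = Φ(1.999) = 97.7%. With all 99 evaluable (66 against 33) the drift is 4.020 and power is 98.0%. Either rounds to the printed 98%, with no interim analysis in the calculation.

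**Step 2: boundaries for three looks.** The information fractions are 30/96 = 0.3125, 60/96 = 0.625 and 1. Cumulative one-sided alpha spent at fraction t is 0.025 × (e^t − 1)/(e − 1):

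- t = 0.3125: 0.025 × 0.3668/1.7183 = 0.0053
- t = 0.625: 0.025 × 0.8682/1.7183 = 0.0126
- t = 1: 0.0250

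Solving for the critical values by recursive numerical integration gives z = 2.553, 2.365 and 2.110. The final test is therefore at a two-sided nominal level of 0.0349.

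**Step 3: power for three looks.** The first look can be checked by hand. With 20 against 10, drift = 3.0/(3.5 × √0.15) = 2.213, and Φ(2.213 − 2.553) = Φ(−0.340) = 36.7%. The integration gives cumulative crossing probabilities of 36.7%, 78.8% and 97.05%. Section 9.2 prints 38%, 78% and 97%, so agreement is within 2 points at the interims, whose sizes are only approximate, and the final figure matches after rounding. If the futility boundary is also followed, the last figure is 96.8%.

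**Step 4: does any reasonable variant reach 98%?**

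| Looks at | Efficacy boundary only | Futility also followed |
|---|---|---|
| 30 / 60 / 96 | 97.05% | 96.8% |
| 32 / 64 / 96 | 97.0% | 96.8% |
| 30 / 60 / 99 (no dropout) | 97.45% | 97.3% |
| 33 / 66 / 99 (no dropout) | 97.4% | 97.2% |

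All round to 97%. The 98% is the power of a single analysis.

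**Step 5: power at the 90-participant minimum.** Evaluable numbers of 90, and of 87 on the assumption that 3 of the 90 have dropped out and contribute nothing:

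| Evaluable | No interim | Both interims, efficacy only | Both interims, futility followed |
|---|---|---|---|
| 90 | 97.0% | 96.1% | 95.8% |
| 87 | 96.5% | 95.5% | 95.1% |

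The summary of changes at the front of the Protocol gives more than 95% for 90 treated participants with the same effect and SD. Every entry agrees with it.

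**The case against.** The gap is small: 97.72% against 97.05% at 96 evaluable. The planned size and both interim sizes are stated as approximate, and no design choice depends on one rounded point. Section 9.2 already separates the figure without interims from the figure with both, so a reader of the statistical section is not misled. All of this stands. It limits the point to one sentence in the Synopsis and to minor importance. It does not remove the point, because the Synopsis names the three-look design and both spending functions as the basis of a figure which that design does not attain.

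A reader might go further and infer that the analysis the protocol will trigger, at 90 participants with discontinuations counted, has only about 95.5% to 96% power, with more than twice the implied type II error. The documents do not support this. That range needs both interims, which are optional, and an analysis at exactly 90, which is a floor while the target stays at about 99. Its lower end also needs all 3 planned dropouts to fall within those 90 and to contribute nothing, although the primary model is a repeated-measures model that uses their earlier visits. Even in that stacked case the type II error is 4.54% against 2.28% for the single analysis at 96, a ratio of 1.99.

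Nor is a final critical level below 0.05 a defect. Section 9.5 says the nominal type I error of the primary analysis will be adjusted if an interim is performed without meeting its objective.

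**Conclusion.** The point holds as a labelling error in Section 1.1. The Synopsis attaches the fixed-design power to the three-look design. The correct figure for that design is 97% (97.05% recomputed, or 96.8% with futility followed), as Section 9.2 says. The overstatement is one rounded point: 97.72 − 97.05 = 0.67 unrounded on the efficacy boundary alone. The recomputation rests on the protocol's own effect, SD, allocation and dropout, with looks at exactly 30, 60 and 96; varying the look times and the final size does not change the rounded answer.

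The trial is not underpowered. The 90-participant trigger contradicts nothing, because the stated power of more than 95% for 90 holds with or without interims.

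**What to change.** Change the power sentence in Section 1.1 in one of two ways:

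- state 97% power with 96 evaluable participants if both interim analyses are performed, and 98% if neither is performed; or
- keep 98% and take the group-sequential design and spending functions out of its list of bases, so that the sentence matches Section 9.2.

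The first is more informative. Section 9.2 needs no correction. Adding the power at the 90-participant minimum to Section 1.1 or 9.2 (about 95.5% to 96% with both interims on the efficacy boundary, 96.5% to 97% with none, for 87 to 90 evaluable) would help a reader but is optional.

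The cost is one sentence. Sample size, boundaries and analysis are untouched; the headline figure becomes one point less favourable when interims are assumed.
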